Faba beans are a rich source of protein, vitamins, minerals and dietary fibre, and are low in fat. They are vegan, genetically modified organism (GMO) free and free of common allergens. Faba bean has a well-balanced amino acid profile, similar to that of the pea and soy (see Table 1) (16). Clinical studies have shown that regular consumption of pulses (including faba beans) can reduce blood levels of total cholesterol and low-density lipoprotein (LDL), and therefore may reduce the risk of CVD. One of the key benefits of FPs over many other plant-based protein powders, including pea protein, is that it has a less grainy (creamier) texture and is more palatable. Overall, there is very little known about the basic digestion of FP in terms of the postprandial amino acid profile and its effect on metabolism after ingestion. This information is fundamental to understand before embarking on longer term human studies. To the best of our knowledge, no other study has examined the specific bioavailability, digestibility, and metabolism of FP compared to WP.

AIM

The aim of this study is to assess the acute effect of FP vs WP, with and without a glucose load, on satiety hormones, postprandial amino acid bioavailability, glucose, insulin and a range of metabolomic markers in circulating blood in healthy volunteers.

MAIN RESEARCH QUESTIONS AND HYPOTHESES BEING ADDRESSED

Question 1 – What effect does FP have on glucagon-like peptide-1 (GLP-1), other satiety hormones, amino acid availability, glucose, insulin and a range of metabolomic markers compared to the same dose of WP in healthy adults?

Hypothesis 1 – A beverage containing FP protein will have a similar stimulatory effect on GLP-1 and satiety hormone secretion but will have lower amino acid availability compared to WP.

Question 2 – What effect does FP together with a glucose load have on GLP-1 and other satiety hormones, amino acid availability, postprandial glycaemic, and insulinaemic response and a range of

metabolomic markers compared to the same dose of WP together with a glucose load in healthy adults?

Hypothesis 2 – A beverage containing FP and glucose will attenuate the postprandial glycaemic response to a greater extent than a beverage containing the same dose of WP and glucose.

STUDY DESIGN OVERVIEW

The study is a single-blind, randomised, acute, crossover intervention trial.

STUDY DESIGN

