Participants will complete four acute interventions (two pairs, as shown in Table 2 below) in a random order with at least a one week washout between studies (four study visits in total, each visit will last 2.5 hours). At each visit, participants will consume one of the four test beverages detailed in Table 2.

Table 2 Details of the four acute interventions provided to participants (one per study visit; four study visits in total)

[figure not shown]
| | | |
|------------------------|----------------|---|
| Pair 1 (WP vs FP) | Intervention 1 | Whey protein, WP; 0.4g/kg body weight |
| | Intervention 2 | Faba bean protein, FP; 0.4g/kg body weight |
| Pair 2 (WPG vs FPG) | Intervention 3 | Whey protein and glucose load, WPG; 0.4g/kg body weight WP + 50g glucose |
| | Intervention 4 | Faba bean protein and glucose load, FPG; 0.4g/kg body weight FP + 50g glucose |

An overview of the study assessments and the participant's journey through the study is shown in Figure 1 and a detailed description of the methods is given below.

In brief, the study will require participants to attend the Northern Ireland Clinical Research Facility (NICRF) at the Belfast City Hospital U-floor on four occasions at least one week apart (Visits 1,2,3,4); each of these visits will last 2.5 hours and participants will consume a beverage consisting of one of the above interventions at each visit.

Figure 1: Overview of participant's journey throughout the study

Four interventions will be delivered in random order: intervention #1 - WP; intervention #2 - FP; intervention #3 – WPG; intervention #4 – FPG.

PARTICIPANTS

A total of 20 healthy participants will be recruited (see sample size section for details). The specific inclusion and exclusion criteria are as follows:

Inclusion criteria

- 18-40 years old
- Healthy volunteers
- Body mass index (BMI) $\geq 18.5 \text{ kg/m}^2$ and/or weight $\geq 50\text{kg}$ (7 Stone 12 pounds) [minimum weight in line with NI Blood transfusion requirements]
- Be willing to consume WP and FP beverages
- Be available to meet the requirements of the study

Exclusion criteria

- Medical condition or medication known to affect glucose regulation or appetite and/or digestion and absorption of nutrients
- Known history of diabetes mellitus or the use of antihyperglycemic drugs or insulin to treat diabetes and related conditions
- Use of steroids, protease inhibitors or antipsychotics

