Compared to a 50g glucose control, Thondre et al. showed that there was a dose response effect of pea protein (25g and 50g) on postprandial glycaemia and stimulated insulin release over a three hour period in healthy adults (14).

RANDOMISATION AND BLINDING

The study will be a four-visit, single-blind, acute crossover study; with at least a one week washout period between visits. A computer-generated randomisation scheme will be prepared by a statistician who is independent of the study team and provided to the researcher who is preparing the test beverages (CK).

The researcher will prepare beverages for each visit for each participant according to the randomisation list. To maintain participant blinding, beverages will be provided in identical opaque containers labelled with the participant number and the intervention period. Thus, the participants will be unaware which beverage they are taking during each visit.

PROPOSED OUTCOMES

Primary endpoint: Circulating concentrations of intact GLP-1 in blood.

Secondary endpoints: Circulating concentrations of other satiety hormones, glucose and insulin concentration, amino acid availability in blood.

Exploratory endpoints: Metabolomic and proteomic markers in blood.

SAMPLE SIZE

Based on variability data from previously published studies in similar populations (6, 8), as well as unpublished data from our own group, a sample size of 16 participants will give the study 80% power to detect a significant difference of 10-15% in total AUC GLP-1 between treatment conditions (WP vs FB; or WPG vs FPG) or a difference in AUC Glucose of 5-15% between treatment conditions (WPG vs FPG).

To allow for dropout, it is anticipated that 20 participants will be recruited.

STUDY ASSESSMENTS

All assessments will be carried out at the Northern Ireland Clinical Research Facility, U Floor, Belfast City Hospital tower block.

Questionnaires (paper copies provided for completion):

All participants will be asked to complete a short lifestyle questionnaire (sex, age, food and drinks, alcohol, physical activity and smoking status (adapted from Leeds Short Form Food Frequency Questionnaire (20)); see Appendix 8.0) at their first visit.

Visual analogue scales (see Appendix 9.0) to rate feelings of hunger will be completed during each study visit at T0 (before the drink is consumed), T30, T60, T90 and T120 (minutes).

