At the end of each visit, participants will be asked to complete an assessment of palatability of the test beverage they consumed (see Appendix 10.0). Using the 9 point hedonic scale (21), we will ask participants to rate the initial and after taste, the texture/feeling in their mouth, and the overall acceptability of the beverage.

Anthropometric data:

At the first visit, weight (kg) and height (m) will be measured using calibrated scales and a stadiometer respectively (see Appendix 11.0). Body mass index (BMI) will be calculated – weight in kilograms divided by height in meters squared.

Waist circumference (inches) will be measured using standard equipment (See Appendix 11.0). It will be measured using a flexible measuring tape designed for this purpose.

Blood samples:

At the start of each visit to the NI Clinical Research Facility, a cannula will be inserted by a trained nurse. Blood samples will be taken at T0 (before the drink is consumed), T30, T60, T90 and T120 (minutes). At each time point, a 4ml EDTA plasma, 2ml Sodium Fluoride plasma and 6ml Serum tube will be collected giving a total volume of 60mls for each study visit.

Participants will be supervised at all times by the research nurse taking the blood samples and the researcher. They will be asked to remain in the NICRF for 15 minutes after the last blood sample has been taken.

All blood samples will be taken from the antecubital vein by the trained nurse at NICRF. Samples will be separated into plasma and serum and stored at -80°C for batch analysis once the study has been completed. Samples will be processed, stored and analysed in the nutrition labs at the Centre for Public Health (CPH).

Participants will be given a snack and a drink to take away at the end of study visit.

LABORATORY METHODOLOGY (Nutrition laboratories, Centre for Public Health)

Assessment of gut hormones

The assessment of gut hormones will be measured by enzyme-linked immunosorbent assay (ELISA). GLP-1 will be carried out using an ELISA kit purchased from EMD Millipore Corporation. Other gut hormones (including GIP, Leptin, Ghrelin and Adiponectin) will be measured by Quantikine ELISA kits (R&D Systems, Minneapolis, MN, USA) as per the manufacturer's instructions. In assay validation, multiple freeze/thaw cycles will be tested

for stability. All assays were performed in duplicate using kits with the same batch number, by operators blinded to sample identity.

Assessment of insulin and glucose levels

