Fasting insulin will be measured by Biochemistry labs at the Royal Victoria Hospital and fasting glucose will be measured using an automated glucose oxidase method using a Beckman glucose analyzer. Fasting glucose and insulin will be used to calculate Homeostatic model assessment (HOMA), a measure of insulin resistance and beta-cell function (22).

Targeted metabolomics analysis (School of Biological Sciences laboratories, Prof [name])

Targeted metabolomics profiling will be performed using a commercially available MxP Quant500 XL kit (Biocrates Life Science AG, Innsbruck, Austria), which quantifies more than 1,000 metabolites and lipids from 26 analyte classes. This process also permits the calculation of >400 “metabolism indicators”. These are pre-determined sums and ratios comprising the quantified metabolites and pertain to specific biological pathways or syntheses.

All frozen plasma or serum samples (-80°C) will be thawed on ice before preparation, according to the instruction from the kit manufacturer. In brief, 10 µL of phosphate-buffered saline, calibrators, quality controls (QCs, lyophilized plasma spiking with metabolites at three known concentrations), and plasma samples will be added to a 96-well plate which contains isotopic-labelled internal standards, followed by adding phenyl isothiocyanate (PITC) to derivatize amino acids and biogenic amines. Metabolite separation will be performed using an ultra-performance liquid chromatography (UPLC) system (AB SCIEX ExionLC system, California, USA) with a reversed-phase MxP Quant 500 UHPLC column and analysed using a triple-quadrupole mass spectrometer (Xevo TQ-S, Waters Corporation, Milford, USA) operating in the multiple reaction monitoring (MRM) mode. All the other metabolites (acylcarnitines, hexoses, glycerophospholipids, and sphingolipids) will be quantified using the same mass spectrometer without column separation by the flow injection analysis (FIA) operating in MRM mode.

For quantitation, both LC and FIA data will be converted and imported directly into the Biocrates software, MetIDQ Oxygen, and quantified. MetIDQ includes an automated simple target normalization procedure based on QC or sample pool for batch-to-batch and kit plate-to-plate correction for sample cohort across several kit plates. Metabolite concentrations will be calculated and expressed as micromole (µM).

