Whenever $\geq 20\%$ of measurements for a metabolite are lower than the limit of detection (LOD), the metabolite will be described as “undetectable” and will be excluded from the analysis. Any metabolism indicators involving undetectable metabolites will not be calculated. The LOD of each metabolite will be based on the Quant500 kit methodology in accordance with the manufacturer’s instructions.

Proteomics analysis (School of Biological Sciences laboratories)

A relative quantification for each of the most abundant ~600 proteins in blood plasma will be performed. Data will be acquired in diaPASEF mode (data independent acquisition – parallel accumulation serial fragmentation) on a timsTOF Pro mass spectrometer equipped with nanoElute chromatography system (Bruker) established in by [name] at QUB

(23). This method uses trapped ion mobility separations to increase sensitivity and resolving power combined with data independent acquisition to ensure quantitative robustness and data completeness. Current data from plasma samples show we can robustly quantify approximately 600 plasma proteins from only 10µl of human plasma. A commercial 96 well plate format sample preparation kit (Preomics iST) will be used to extract proteins from plasma, digest these to peptides, and clean-up by solid phase extraction resulting in injection-ready samples. Analysis of mass spectrometry data to produce protein-level quantitative data matrices will be performed using Spectronaut software.

STATISTICAL ANALYSIS

Statistical Analysis will be carried out using SPSS software for Windows, version 29. Statistical advice will be given by [name], a medical statistician from the Centre for Public Health.

The data will be presented as mean, standard deviation (SD) and standard error of the mean (SEM) values. Before statistical analysis, the normality of the data was tested using the Shapiro–Wilk statistic.

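### The 20% detection filter pools all drinks and times, so it can discard metabolites that appear only after one protein before the proteins are compared (exploratory metabolomics; minor)

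*Protocol*

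**What the plan says.** The rule is in the Protocol under Laboratory Methodology, at the end of the targeted metabolomics text. When 20% or more "of measurements for a metabolite are lower than the limit of detection (LOD), the metabolite will be described as" undetectable, and it is left out of the analysis. The loss carries over to derived quantities: "Any metabolism indicators involving undetectable metabolites will not be calculated". The rule does not separate interventions or time points, and it has no exception for a compound absent when fasting or after one of the proteins.

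The design is fixed elsewhere in the Protocol:

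- Study Design, caption to Figure 1: "Four interventions will be delivered in random order: intervention #1 - WP; intervention #2 - FP; intervention #3 – WPG; intervention #4 – FPG".
- Study Assessments, Blood samples: "Blood samples will be taken at T0 (before the drink is consumed), T30, T60, T90 and T120 (minutes").
- Targeted metabolomics analysis: "All frozen plasma or serum samples (-80°C) will be thawed on ice before preparation". No restriction to selected time points is given.
- Aim: the acute effect of faba versus whey protein is to be assessed on, among other things, "a range of metabolomic markers in circulating blood in healthy volunteers".

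The Statistical Analysis section classes the metabolomic work as exploratory.

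**The concern.** A filter on the overall share of non-detects is meant to remove analytes that the assay cannot measure reliably. It does that well when all samples come from the same condition. Here the samples come from four drinks and from before and after each drink, and absence under some of those conditions may be the effect of interest. A compound that separates the two proteins perfectly, always found after faba and never after whey, would be labelled undetectable and not examined. The filter therefore depends on the treatment effect: it keeps compounds seen throughout and can remove those that switch on or off with the protein. In an analysis meant to generate hypotheses, such differences should not be discarded before anyone has looked at them.

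**Working it through.** **Inputs.** Four interventions, two with faba bean (Table 2 and Figure 1 caption). Five samples per visit, one before the drink and four after (Blood samples). Participants: 20 recruited ("A total of 20 healthy participants will be recruited") and 16 in the power statement ("a sample size of 16 participants will give the study 80% power"). Threshold: excluded if 20% or more are below the limit of detection (LOD), with 20% itself included.

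**Check of the sample count against the protocol's own figures.** Each time point uses 4 + 2 + 6 = 12 ml. Then 5 × 12 = 60 ml per visit and 4 × 60 = 240 ml in total, which are the two volumes the protocol states. So there are 5 × 4 = 20 samples per complete participant: 20 × 20 = 400 for 20 participants and 16 × 20 = 320 for 16.

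**Formula.** Share below LOD = (20 − samples with the metabolite detected) / 20. The number of participants cancels when data are complete.

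| Pattern of detection | Detected of 20 | Share below LOD | Result |
|---|---|---|---|
| After a single drink only, all post-drink times | 4 | 16/20 = 80% | excluded |
| After FP and FPG only, all post-drink times | 2 × 4 = 8 | 12/20 = 60% | excluded |
| After every drink, but only from T60 | 4 × 3 = 12 | 8/20 = 40% | excluded |
| After every drink from T30, never at T0 | 4 × 4 = 16 | 4/20 = 20% | exactly at the limit, excluded |
| Everywhere except after a single drink | 20 − 4 = 16 | 4/20 = 20% | exactly at the limit, excluded |

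In the last row the missing samples are the four post-drink ones. That visit's T0 sample is taken before the drink and cannot depend on it, so counting the whole visit (5/20 = 25%) would be wrong. If the compound is also absent when fasting, the four T0 samples are added: 8/20 = 40%.

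**How firm the boundary case is.** Let q0 be the non-detect rate at T0 and q1 the rate after the drink. The overall share is 0.2·q0 + 0.8·q1, and exclusion needs this to reach 0.2.

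- q0 = 1, q1 = 0: share 0.20 (80/400 or 64/320), excluded.
- One T0 sample above LOD, q1 = 0: 79/400 = 19.75%, or 63/320 = 19.69%, kept.
- q0 = 0.9: exclusion needs q1 ≥ (0.2 − 0.18)/0.8 = 2.5%.
- q0 = 0.5: exclusion needs q1 ≥ (0.2 − 0.1)/0.8 = 12.5%.

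The T0-only pattern can tip either way on a few samples. The faba-only pattern cannot: at 60% it is three times the threshold.

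**The case against.** Several points against the concern have force.

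- **Scope.** A reader might infer that the rule removes the very markers the trial was set up to find. The documents do not support that. The primary endpoint is intact GLP-1. GLP-1 and the other gut hormones are measured by ELISA, and glucose and insulin by separate methods, so none of them passes through this filter. Amino acid availability is a secondary endpoint and this kit is the only amino acid assay described, so the rule formally covers it. But nothing suggests that any amino acid falls below LOD, and Table 1 lists the same measured amino acids for whey and faba bean (aspartic acid was measured only for faba).
- **Number affected.** The kit is a fixed targeted panel. The protocol names no panel analyte that is specific to faba bean or absent when fasting, so the number lost could be zero. This stands.
- **Bias.** A reader might also infer that the metabolomic comparison is biased towards no difference. It is not, in the usual sense. A dropped metabolite is not tested and not reported as equal, the estimates for the others are unchanged, and p-values are not adjusted for multiplicity, so no threshold moves. What can be lost is a discovery.
- **T0 as the cause.** The observation that T0 samples make up 20% of all samples explains only the boundary pattern, which one T0 detection reverses. That pattern is also not in itself a contrast between proteins. The argument should rest on the faba-only and single-drink cases.
- **Detail for the SAP.** The denominator of a detection filter could be settled in an SAP, which was not available here. But the protocol does not leave the matter open. It states a rule and its consequence, and that rule suits this design badly.

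**Conclusion.** The point holds as a minor one. On its plain reading the rule pools all samples. A panel metabolite found only after the faba drinks (60% below LOD), only after one drink (80%), or only from T60 (40%) would be excluded before faba and whey are compared, along with its metabolism indicators. Two further patterns fall exactly on the 20% limit.

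This rests on three assumptions:

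- No split by intervention or time is intended; none is written.
- All five time points are assayed. The protocol implies this without stating it. If fewer times were assayed with T0 among them, the T0 share would exceed 20%.
- Data are complete. This matters only for the boundary patterns.

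The consequence is limited to possible missed on/off differences in an exploratory analysis.

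**What to change.** Apply the threshold within groups, with one retention rule. The groups are T0 pooled over the four visits, plus each of the 4 × 4 = 16 intervention-by-post-drink-time cells, 17 in all. Keep a metabolite if at least 80% of samples are above LOD in at least one group; exclude it only if it fails in all 17. A faba-only metabolite then passes in 8 groups and is kept. Exactly 80% detection counts as a pass, whereas the present rule excludes at exactly 20% non-detection; the text should say so.

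Analyse retained metabolites with many values below LOD as detected/not detected, or with a censored-data method. Fix this before the metabolomic data are seen.

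**Cost.** A sentence or two in the protocol or SAP, with no new samples or assays. The real cost is more censored metabolites to analyse, and some borderline ones kept by chance because cells hold only 16 to 20 samples. As an illustration, assume a true detection rate of 60% in every cell. A 16-person cell passes with 13 or more detections (0.8 × 16 = 12.8), which has binomial probability of about 6.5%. If the 16 post-drink cells were independent, at least one would pass with probability 1 − 0.935^16, about 66%. Correlation within participants would change this figure.

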Primary and secondary endpoints will be analysed using repeated measures ANOVA (for normally distributed data) and non-parametric Friedman test (where data were not normally distributed) to compare concentrations at each time point. Incremental Area under the Curve (iAUC) (at 30, 60, 90 and 120 min) will be calculated and reported along with peak concentration and time of peak concentration for relevant endpoints in response to each of the interventions. Post hoc analyses will be performed using the Bonferroni correction for parametric data and the Wilcoxon signed-rank test for non-parametric data. Statistical significance will be set at p value ≤ 0.05 for all tests.

Metabolomic and proteomic analysis will be considered exploratory analysis. P-values will not be altered for multiple testing, but findings will be treated as hypothesis generating rather than hypothesis testing.

PROPOSED TIMELINE FOR THE STUDY

January – February 2024 – Obtain ethical approval; study set-up

February – March 2024 – Recruitment

February – June 2024 – Completion of dietary interventions

July-December 2024 – Laboratory analysis, statistical data analysis and write-up

STUDY PHONE NUMBER AND EMAIL ADDRESS

To ensure personal telephone numbers are not given out we have obtained a mobile phone unique to the study.

Contact information for study participants:

Email address: [contact] or [contact]

[contact]

ETHICAL CONSIDERATIONS

The study will be carried out in accordance with the declaration of Helsinki. Ethical approval will be obtained from the Faculty of Medicine, Health and Life Sciences Research Ethics Committee at Queen's University Belfast. Participants will be given full details of the study and will have the opportunity to ask questions. All participants will provide written informed consent prior to participation and will be informed that they can withdraw from the study at any time without having to give a reason. Participants will be informed that any data or samples provided up to the point of withdrawal may be included in the study unless they request otherwise. Participants can also request withdrawal of their data or samples at any time after completion of the study by contacting the Chief Investigator; any data or samples that have been analysed or reported at the time of request will not be able to be retracted.

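### The named test for the primary and secondary endpoints makes no use of each visit's pre-drink sample as a baseline covariate, and could lose power further if that sample is averaged into the beverage effect

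*Protocol*

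**What the plan says.** The Protocol lists under PROPOSED OUTCOMES: "Primary endpoint: Circulating concentrations of intact GLP-1 in blood". It names no summary measure or time point there.

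Under STUDY ASSESSMENTS, Blood samples: "Blood samples will be taken at T0 (before the drink is consumed), T30, T60, T90 and T120 (minutes". Each of the four visits thus has its own baseline and four post-drink samples.

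Under STATISTICAL ANALYSIS: "Primary and secondary endpoints will be analysed using repeated measures ANOVA (for normally distributed data", with Friedman as the alternative for non-normal data, in both cases "to compare concentrations at each time point". No baseline covariate is named. The next sentence reads "Incremental Area under the Curve (iAUC) (at 30, 60, 90 and 120 min) will be calculated and reported", together with peak and time of peak. Post hoc work uses Bonferroni on the parametric branch and Wilcoxon signed-rank on the other.

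Under SAMPLE SIZE: "a sample size of 16 participants will give the study 80% power to detect a significant difference of 10-15% in total AUC GLP-1". Total AUC includes the T0 sample and is not corrected for it.

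**The concern.** In a crossover the participant's stable level cancels, but the fasting level still moves from one visit to the next. If a visit that starts high tends to stay high, part of the noise in the post-drink comparison can be predicted from that visit's T0. An analysis of raw concentrations leaves this part in the error term, although the sample that would remove it is already being taken.

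A second loss is conditional. Beverages cannot differ at T0 except by chance. If T0 is one of the levels averaged into the beverage main effect, one guaranteed null is averaged with four possible effects.

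The direction matters for the primary endpoint. Hypothesis 1 expects the two proteins to stimulate GLP-1 similarly, so a test short of power makes a non-significant result more likely, and that result could be misread as support.

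**Working it through.** **The plan's own figure.** No SD is printed, so 16 can only be back-solved. For a paired comparison at two-sided 0.05 (sidedness is not stated), 80% power with n = 16 needs a standardised difference d = 0.749 by noncentral t. This implies an SD of the paired difference of 10/0.749 = 13.3% for a 10% difference, or 15/0.749 = 20.0% for 15%. The sample size is neither confirmed nor shown wrong. Allowing for dropout, 16/0.8 = 20 agrees with the recruitment target.

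**Set-up.** Take the within-person difference between two beverages at each time, scaled to variance 1, with correlation r between any two times. The values of r are assumptions; the Protocol gives none. The effect is 0 at T0 and δ at each post-drink time. Set δ so that the unadjusted mean of T30 to T120 has 80% power: δ = 0.749·√v4, where v4 = (1+3r)/4.

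**Formulas.**
- Main effect over five times: effect 0.8δ, variance v5 = (1+4r)/5.
- Post-drink mean with T0 as covariate: effect δ, variance v4 − r².
- Post-drink mean minus T0: effect δ, variance v4 + 1 − 2r.
- Each d is effect/√variance. Power comes from the noncentral t with noncentrality d·√16.

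| | r = 0.1 | r = 0.3 | r = 0.5 |
|---|---|---|---|
| v4 | 0.325 | 0.475 | 0.625 |
| Unadjusted post-drink mean (set) | 80% | 80% | 80% |
| v5 | 0.280 | 0.440 | 0.600 |
| T0 as fifth level: d, power | 0.646, 68% | 0.623, 64% | 0.612, 63% |
| v4 − r² | 0.315 | 0.385 | 0.375 |
| T0 as covariate: d, power | 0.761, 81% | 0.832, 87% | 0.968, 95% |
| v4 + 1 − 2r | 1.125 | 0.875 | 0.625 |
| Minus T0: d, power | 0.403, 33% | 0.552, 54% | 0.749, 80% |

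**Small-sample cost.** The covariate row treats the slope as known. Estimating it from 16 pairs inflates the variance by about 1 + 1/(16−3) = 1.08 on average. A simulation of that two-beverage analysis (20,000 runs per value of r) gives about 78%, 84% and 93%. A slope estimated from all four visits should cost less.

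**One post-drink time.** T0 does not enter, so there is no dilution. If such a comparison has 80% power, the covariate reduces its variance to 1 − r² = 0.99, 0.91, 0.75. Power becomes about 80%, 83% and 90% by formula, and 77%, 81% and 87% in simulation.

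**Interaction.** With a flat post-drink effect, the unadjusted beverage-by-time test has simulated power of 38%, 62% and 93% with T0 included, against about 5% without it (r = 0.3, 0.5, 0.7).

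**Total AUC.** By the trapezoid rule T0 carries 15/120 = 12.5% of the weight, less than the 20% it has in a plain five-point mean.

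**The case against.** Much of the opposing case stands, and it rules out stronger readings.

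- A reader might infer that the Protocol makes T0 an outcome, tests it between beverages and counts it in the Bonferroni family. It says none of this. Reading T0 into the phrase about time points is natural, but it is an inference. The chance of a spurious T0 finding is equally conditional: 1 − 0.95² = 9.75% for two unadjusted pair tests, but 1 − 0.99² = 2% if Bonferroni covers five times.
- A reader might infer that the beverage effect is diluted throughout. Dilution affects only a main effect averaged over all five samples, and the Protocol does not name that as the test. Comparisons at T30 to T120 are untouched, and an unadjusted interaction test gains from keeping T0.
- A reader might infer that the baseline goes unused. Incremental AUC is measured from T0, and fasting glucose and insulin feed HOMA.
- Friedman and Wilcoxon tests take no covariate, so the remedy changes the method and is more than an added clause.

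It could also be said that the handling of T0 belongs in a statistical analysis plan. That would answer mere silence. Here the Protocol does fix a test for every primary and secondary endpoint, on unadjusted concentrations. Incremental AUC does not fill the gap: it is to be calculated and reported with no test attached, and in the table above subtracting T0 does worse than ignoring it when r is below 0.5.

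**Conclusion.** The point holds in a limited form. The named test leaves visit-to-visit fasting variation in its error although a baseline is collected at every visit. Adjustment would raise power from 80% to about 87% at r = 0.3 and 95% at r = 0.5 by formula (84% and 93% in simulation). At r = 0.1 it makes next to no difference: 81% by formula, 78% in simulation.

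Only if T0 is a level and the beverage main effect is the test does power also fall to about 63–68%. The documents do not settle whether that is the plan, so it should not be reported as what the Protocol does.

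The figures rest on assumed correlations that are equal across times, a flat post-drink effect, two-sided 0.05, 16 evaluable participants, and a starting 80% for the post-drink mean, not for the total AUC used in sizing. This is a recommended improvement. It does not show that the trial is wrongly sized.

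**What to change.** For each primary and secondary endpoint, analyse the T30 to T120 concentrations (or the post-drink AUC) in a linear mixed model. Include beverage, time, beverage-by-time and period as fixed effects, participant as random effect, and the same visit's T0 value as covariate. Let samples from one visit be correlated, so that they are not counted as independent. State that the baseline-adjusted WP–FP and WPG–FPG contrasts, and not the interaction alone, are the tests. A flat effect does not show in an interaction limited to post-drink times.

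Do not test beverages at T0, and leave T0 out of any Bonferroni family. Where normality fails, transform within this model (for example by logarithm), with T0 on the same scale.

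If total AUC is kept to match the sample size section, enter T0 as covariate there too. On the untransformed scale the T0 part of the AUC is then absorbed by the covariate, and the beverage contrast equals that for the post-drink part.

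Cost: the named ANOVA and its non-parametric alternative give way to a mixed model, one degree of freedom is spent on the covariate, and there is little or no gain if the within-visit correlation is near zero. No new samples are needed.
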